3.3. Disposition

The number and percentage of subjects completing or prematurely discontinuing the study including reasons for discontinuation will be summarized overall and by treatment group for the following:

- Subjects who were randomized
- Subjects in the Safety Population
- Subjects in the FAS Population
- Subjects who completed the double-blind treatment period
- Subjects who discontinued the study during the double-blind treatment period along with reasons for discontinuation

3.4. Protocol Deviation

Subjects with major protocol deviations using the following categories will be summarized by treatment group along with supportive listings for each category.

- Did not meet the inclusion/exclusion criteria
- Received prohibited medications
- Lack of adherence with study medication, as defined by subjects taking less than 70% of the protocol specified amount of study medication
- Randomization or dosing error

3.5. Demographics and Baseline Characteristics

Demographics and baseline characteristics such as sex, age, race, ethnicity, weight, and body mass index (BMI) will be summarized overall and by treatment group for the Safety and FAS Population.

Baseline efficacy characteristics, eg, PANSS and CGI-S, will be summarized by treatment group for the FAS Population to assess the comparability of the treatment groups.

Medical and psychiatric history will be summarized for the Safety Population by treatment group and overall.

3.6. Prior and Concomitant Medication

Prior medications are defined as medications taken prior to the first dose of study drug. Concomitant medications are defined as medications taken on or after the first dose of study drug. All medications as documented by the investigator will be coded using the World Health Organization Anatomical Therapeutic Chemical (WHO-ATC) drug dictionary Enhanced Extended with Herbal version WHODRUG_C / 161E+H.

Prior and concomitant medications will be summarized by the preferred drug name for the Safety population. Concomitant medications that are taken during the double-blind treatment period will be included in the summary table. For the summary tables, if a subject has taken a prior or concomitant medication more than once, the subject will be counted only once for the medication. All reported medications (including those initiated after the last dose of double-blind study medication) will be included in the listing.

3.7. Treatment Adherence Rate and Extent of Exposure

3.7.1. Treatment Adherence Rate

Treatment adherence to the daily dosing schedule during the double-blind treatment period will be summarized by treatment group for the Safety Population. Treatment adherence will be calculated as follows:

$$100 \times \frac{\text{Total tablets dispensed} - \text{total tablets returned} - \text{total tablets lost}}{\text{Total tablets scheduled to be taken}}$$

3.7.2. Duration of Study Drug Administration

Duration of study drug administration is defined as the number of days from the date of the first dose of study drug taken to the date of the last dose taken, inclusive (ie, last dose date – first dose

date + 1). Duration of study drug administration will be summarized for the Safety Population by treatment group.

The overall prescribed mean and modal dose of olanzapine will be summarized by treatment group for relevant treatment groups. Number and percentage of subjects will be summarized by their final dose level.

3.8. Efficacy Analyses

3.8.1. General Considerations

All statistical tests will be 2-sided hypothesis tests performed at the 5% significance level. All confidence intervals will be 2-sided 95% confidence intervals.

Baseline is defined as the last non-missing observation on or before the first dose of study drug in the double-blind treatment period.

Unless specified otherwise, all formal comparisons will be between ALKS 3831 and placebo groups. An exploratory analysis will be conducted between olanzapine and placebo groups.

3.8.2. Primary Efficacy Endpoint

The primary efficacy endpoint is change from baseline in PANSS total score at Week 4.

3.8.2.1. Primary Analysis

For the primary efficacy endpoint, change from baseline in PANSS total score at Week 4, primary analysis will be carried out using a mixed model with repeated measurements (MMRM) with an unstructured variance-covariance matrix based on the observed data for the FAS population. The model will include region (US vs. non-US), visit, treatment, and interaction term of visit and treatment as categorical variables, and baseline PANSS total score as a covariate. The Kenward-Roger approximation² will be used to adjust the denominator degree of freedom. The change from baseline in PANSS total score at Week 4 in the ALKS 3831 group will be compared to that in the placebo group using superiority testing at two-sided alpha level of 0.05. The least squares (LS) mean, standard error (SE), and LS mean difference between ALKS 3831 and placebo along with the 95% CI, will be summarized.

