### 14.4.1. Primary Endpoint

The primary efficacy endpoint is change from baseline in PANSS total score at Week 4.

For the primary efficacy endpoint, change from baseline in PANSS total score at week 4, analysis will be carried out using a mixed model with repeated measurements (MMRM) with an unstructured variance-covariance matrix based on the observed data. The model will include visit, treatment, and interaction term of visit and treatment as categorical variables, and baseline PANSS total score as a covariate. The statistical test will be carried out as follows:

The change from baseline in PANSS total score at Week 4 in ALKS 3831 group will be compared to that in the placebo group using superiority testing at two-sided alpha level of 0.05.

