2. SAMPLE SIZE CONSIDERATION

The planned sample size is 390 subjects in total, 130 subjects per treatment group. This sample size will provide at least 90% power to show superiority of the ALKS 3831 group compared to placebo group at a 2-sided alpha level of 0.05, assuming a 10-point improvement of PANSS total score at week 4, a standard deviation (SD) of 20, and a dropout rate of 30%.

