3.8.3. Key Secondary Endpoint

The key secondary efficacy endpoint is change from baseline in CGI-S at Week 4.

Primary Analysis

An MMRM analysis, similar to the primary analysis on primary endpoint ([Section 3.8.2.1](#)) will be conducted to analyze the difference between ALKS 3831 and placebo groups.

Sensitivity Analysis

To assess the impact of missing data, a Delta-adjusted Pattern Mixture Model³ similar to the sensitivity analysis of the primary endpoint in [Section 3.8.2.2](#) will be conducted.

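### The primary MMRM fits one baseline PANSS slope to all four visits although only Week 4 is tested; if the slope drifts over time, some Week 4 precision can be lost, and a baseline-by-visit term avoids this at almost no cost

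*SAP*

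**What the plan says.** Protocol 14.4.1 states: "The model will include visit, treatment, and interaction term of visit and treatment as categorical variables, and baseline PANSS total score as a covariate". SAP 3.8.2.1 adds region and otherwise keeps the same terms, ending with "interaction term of visit and treatment as categorical variables, and baseline PANSS total score as a covariate". It specifies "an unstructured variance-covariance matrix based on the observed data for the FAS population". SAP section 5 reports region as the only change to the efficacy models. Neither document contains a baseline-by-visit interaction.

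PANSS is scheduled after baseline on Days 8, 15, 22 and 29 (Protocol 8.2, Table 1). The hypothesis test concerns Week 4 alone.

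For CGI-S, SAP 3.8.3 specifies "An MMRM analysis, similar to the primary analysis on primary endpoint", so the same structure carries over to the key secondary endpoint.

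Two parts of SAP 3.8.2.2 bear on the point. The delta-adjusted analysis imputes visit by visit and then fits an ANCOVA to Week 4 change, so it has its own Week 4 baseline slope. The same section also lets the MMRM take further covariates or factors, but names none.

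**The concern.** The treatment effect may differ from visit to visit, but the dependence of change on baseline may not. If that dependence strengthens between Week 1 and Week 4, a common slope is too shallow at Week 4, the one visit that decides the trial. Two things follow. The part of the baseline effect that is not removed stays in the Week 4 residual variance and widens the confidence interval. And if the arms differ at baseline by chance, the Week 4 estimate is only partly corrected for it. What is at stake is a modest amount of efficiency in the primary and key secondary comparisons, not their validity.

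**Working it through.** **Inputs from the documents (SAP section 2).** 130 per arm, 30% dropout, two-sided alpha 0.05, "assuming a 10-point improvement of PANSS total score at week 4" and "a standard deviation (SD) of 20". The stated result is "This sample size will provide at least 90% power to show superiority".

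**Reproducing the plan's figure.** Evaluable per arm: 130 × 0.70 = 91. SE = 20 × √(2/91) = 2.965. Noncentrality = 10/2.965 = 3.373. Power is 91.8% by noncentral t and 92.1% by the normal approximation. For 90% power, 85 evaluable per arm are needed, and 85/0.7 rounds up to 122, below 130. The claim of at least 90% holds.

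**Inputs that have to be assumed.** Baseline SD 8 to 12 (entry requires PANSS of at least 80, but no SD is given); slopes of change on baseline by visit; residual SDs by visit reaching 20 at Week 4; correlations of 0.6 to 0.8, autoregressive (AR) or compound symmetric (CS); 30% monotone dropout.

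**Formulas.** With residual covariance S, the common slope b is a weighted mean of the visit slopes. The weights are proportional to S⁻¹1, summed over dropout patterns. Relative inflation of Week 4 variance = (slope at Week 4 − b)² × (baseline SD)² / 20².

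**Moderate drift, slopes -0.1, -0.2, -0.3, -0.4:**

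| Residual SDs, correlation | Weights, Weeks 1/2/3/4 | b | Inflation at baseline SD 8 / 10 / 12 |
|---|---|---|---|
| 11, 15, 18, 20; AR 0.8 | 1.11 / -0.15 / -0.02 / 0.06 | -0.10 | 1.4% / 2.3% / 3.3% |
| 11, 15, 18, 20; CS 0.6 | 0.91 / 0.17 / -0.01 / -0.07 | -0.10 | 1.5% / 2.3% / 3.4% |
| 15 rising to 20; AR 0.8 | 0.79 / 0.05 / 0.00 / 0.16 | -0.15 | 1.0% / 1.5% / 2.2% |
| 20 throughout; AR 0.8 | 0.47 / 0.11 / 0.11 / 0.31 | -0.22 | 0.5% / 0.8% / 1.1% |
| 20 throughout; CS 0.6 | 0.34 / 0.26 / 0.22 / 0.18 | -0.22 | 0.5% / 0.8% / 1.1% |

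First row in full: b = 1.11(-0.1) − 0.15(-0.2) − 0.02(-0.3) + 0.06(-0.4) = -0.099. The gap at Week 4 is 0.301, and 0.301² × 100/400 = 2.3% at baseline SD 10. A wider set of covariances, with Week 1 SD down to 9 and correlation up to 0.8, gave up to 5.4%.

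**Strong drift, slopes -0.1, -0.3, -0.5, -0.7.** Every gap doubles, so each inflation is four times as large: from about 4 × 0.5 = 2% (flat SDs, baseline SD 8) to about 4 × 3.4 = 13.6%, or roughly 14% (growing SDs, baseline SD 12). The most extreme covariance in the wider set would give 4 × 5.4 = 21.6%.

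**Equal slopes.** The gap is zero, and so is the inflation.

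**Power, taking SD 20 as the residual SD.** The noncentrality is divided by √(1 + inflation):
- 3%: 3.373/√1.03 = 3.323, power 91.1%
- 10%: 3.373/√1.10 = 3.216, power 89.2%
- 14%: 3.373/√1.14 = 3.159, power about 88%
- 21.6%: 3.373/√1.216 = 3.059, power about 86%

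**Chance imbalance.** With baseline SD 10 and 130 per arm, one SE is 10 × √(2/130) = 1.24 points. With a slope gap of 0.30, 1.24 × 0.30 = 0.37 PANSS points stay uncorrected. At 1.96 SE it is 2.43 × 0.30 = 0.73.

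**Simulation of both models** (3 × 130 subjects, four visits, about 33% dropout at random, SDs 11 to 20, AR 0.8, 400 runs per scenario). Model-based variance ratio, common over by-visit slope: 1.000 for equal slopes; 1.022 for drift to -0.4 with baseline SD 10; 1.089 and 1.129 for drift to -0.7 with baseline SD 10 and 12. Mean estimates were -10.0 to -10.3 for a true -10 under both models, and for the common-slope model average SEs were close to the empirical SDs. With 400 runs, simulated power is good only to 1 to 1.5 points, so the analytic figures are the better guide to size.

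The documents give no effect size or SD for CGI-S, so no figure is offered there.

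**The case against.** The strongest reply is that nothing here is an error. Protocol and SAP agree on the baseline term, the one model change is disclosed, and a single baseline covariate is a legitimate prespecified choice. Randomization keeps the Week 4 contrast valid. The loss needs slopes that drift, which the documents do not report, and it shrinks when visit variances are flat. The uncorrected fraction of a chance imbalance is already reflected in the SE. All of this stands, and it is why the point is minor.

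A reader might go further and infer that the slope is dominated by early visits, that precision is certainly lost, or that the power claim fails. The documents support none of these:
- Near-total weight on Week 1 arises only when variance grows over time. With flat SDs and 30% dropout, Week 4 keeps up to about 0.31, and without dropout it is weighted as heavily as Week 1 under either correlation pattern.
- With equal slopes there is no loss at all.
- SAP section 2 does not say whether SD 20 is before or after baseline adjustment. If it is before, the common slope still improved on no adjustment in every scenario tried.

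A further reply is that SAP 3.8.2.2 already covers this through its Week 4 ANCOVA. It does so only in part. That analysis is not the primary test, and its smallest shift is 10% of the observed difference, with no zero-shift run. A gap between it and the primary result would therefore mix the slope specification with the missing-data assumption. The permission to add unnamed covariates prespecifies nothing.

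**Conclusion.** The point holds as a conditional efficiency issue. The primary model does impose one baseline slope on four visits. If the true slope drifts, Week 4 has a minority weight in it: at most about 0.31 with 30% dropout, and near zero if variance grows. Under the assumed inputs the Week 4 variance inflation is 0% for equal slopes, about 0.5 to 5% for drift from -0.1 to -0.4, and about 2 to 14% for drift to -0.7 over the main set of covariances. The most extreme combination goes beyond that range. Moderate drift costs about one power point or less in most of the cases tried, leaving about 91%. Strong drift can bring power to 88 to 89%, and then only if SD 20 is the residual SD. The treatment estimate is unbiased over randomization and the test is valid. The figure of at least 90% reproduces and is not contradicted. This is an inexpensive optional improvement, not a defect that must be repaired.

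**What to change.** Before unblinding, add a baseline PANSS total score-by-visit fixed effect to the MMRM in SAP 3.8.2.1. In SAP 3.8.3, name baseline CGI-S as the covariate and add its interaction with visit. Record both changes in SAP section 5 beside the region change. The cost is 3 degrees of freedom per model and negligible precision if the slopes turn out equal (simulated variance ratio 1.000). No change to data collection or sample size is needed. The primary model would then also have a Week 4 baseline slope, as the ANCOVA in SAP 3.8.2.2 does, so comparing the two would say more about missing data.

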3.8.2.2. Sensitivity Analysis

To assess the robustness of the primary analysis of the primary endpoint, the following sensitivity analyses will be performed:

- Delta-adjusted Pattern Mixture Model³ will be conducted to assess the impact of missing data. It incorporates the clinical assumption that ALKS 3831 subjects who discontinue at a given time point would have, on average, their unobserved PANSS worsened by some amount δ compared with the observed PANSS of subjects on the same treatment arm who continue to the next timepoint. Subjects who discontinue from the placebo arm would have the same PANSS trajectory as the placebo subjects who stay on the study. A sequential regression-based multiple imputation (MI) procedure will be used to incorporate the assumption and to allow uncertainty in the imputations to be reflected appropriately in the analysis. The imputation model will

include the measurement at the current timepoint as the response variable, and region (US vs. non-US) as factor, the measurements at the previous timepoints and the baseline as covariates. Twenty imputations will be carried out. For each of the 20 imputed data sets, the ANCOVA model with region (US vs. non-US) and treatment group as factors and baseline PANSS as covariate will be fitted to the change from baseline at Week 4 to obtain the treatment effect estimate and standard error. Rubin's rule will be used to combine the treatment effect estimates and standard errors across imputations. The shift parameters to be used in the sensitivity analysis will account for 10%, 20%, 30%, 40%, and 50% of the observed treatment difference between ALKS 3831 and placebo.

- The MMRM model may adjust for additional covariates and/or factors.

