7.1. Reporting Precision

Summary statistics will be presented to the following degree of precision, unless otherwise specified:

Table 9: Degree of Precision

Statistics	Degree of Precision
Mean, Median, Confidence limit boundaries	One more than the raw data, up to 3 decimal places.
Standard deviation, Standard error	One more than the mean, up to 3 decimal places.
Minimum, Maximum	The same as the raw data, up to 2 decimal places.
p-value	Rounded to 3 decimal places and therefore presented as 0.xxx; p-values smaller than 0.001 as '<0.001'; p-values greater than 0.999 as '>0.999'.
Percentage	One decimal place. A percentage of 100% will be reported as 100%. Percentages of zero will be reported as 0.

Fractional numeric values will be presented with a zero to the left of the decimal point (for example, 0.12-0.30).

For weight, height, and BMI, one decimal place will be used for summary statistics.

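### With 20 imputations and no seed in the SAP, a delta-adjusted p-value near 0.05 moves about 2.5- to 4-fold between seeds, so the shift at which significance is lost can partly reflect the seed

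*SAP*

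**What the plan says.** SAP Section 3.8.2.2 specifies a delta-adjusted pattern mixture model for the Week 4 PANSS change. The method is stated as "A sequential regression-based multiple imputation (MI) procedure will be used to incorporate the assumption", and the number of imputed data sets as "Twenty imputations will be carried out". Each imputed data set is analysed by ANCOVA, and "Rubin's rule will be used to combine the treatment effect estimates and standard errors across imputations". The penalty applies to ALKS 3831 dropouts only: "The shift parameters to be used in the sensitivity analysis will account for 10%, 20%, 30%, 40%, and 50% of the observed treatment difference". SAP Section 3.8.3 calls for a similar analysis of CGI-S.

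SAP Section 7.1 gives the display rule for p-values: "Rounded to 3 decimal places and therefore presented as 0.xxx", with anything below 0.001 printed as <0.001. Means and confidence limits carry one decimal more than the raw data, so 0.1 point for PANSS.

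The SAP gives no seed, no limit on Monte Carlo error and no reason for choosing 20. Section 8 leaves programming specifications to a separate document that is not among those available. The SAP also does not say whether the five shift levels share one set of imputation draws.

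**The concern.** The purpose of the five shifts is to see how far the result weakens as the assumption about dropouts becomes harsher. The answer is read from the estimate, interval and p-value at each level. Multiple imputation adds its own random error, which shrinks only as the number of imputations grows. If that error is comparable with the change from one shift level to the next, the level at which significance is lost is partly an accident of the random numbers. Readers would then see a tipping point that another seed would have placed elsewhere.

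**Working it through.** **The plan's own figure.** Inputs from SAP Section 2: "The planned sample size is 390 subjects in total, 130 subjects per treatment group", "assuming a 10-point improvement of PANSS total score at week 4, a standard deviation (SD) of 20, and a dropout rate of 30" percent, two-sided alpha 0.05. Per arm, n = 2 × (20/10)² × (1.960 + 1.282)² = 84.1, so 85. Dividing by 0.7 gives 122 per arm, 366 in total. With 130 × 0.7 = 91 completers per arm, the standard error is 20 × √(2/91) = 2.96 and power is Φ(10/2.96 − 1.96) = 0.92. The claim of "at least 90% power to show superiority of the ALKS 3831 group compared to placebo group at a 2-sided alpha level of 0.05" is reproduced.

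**Monte Carlo error of the pooled t.** Let m be the number of imputations, B the between-imputation variance, T the total variance and λ the fraction of missing information, about B/T.

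1. The pooled estimate varies between seeds with variance B/m. In units of t this is an SD of √(λ/m).
2. The estimate of B is itself noisy, with relative SD √(2/(m−1)). This moves t by t × ½ × λ × √(2/(m−1)).
3. The total SD of t is the root of the sum of squares.

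At m = 20 and t = 2.0:
- λ = 0.15: √(0.0866² + 0.0487²) = 0.099. With 172 degrees of freedom (Barnard-Rubin, complete-data df 256), the 95% range of p is 0.030 to 0.073, or 2.5-fold.
- λ = 0.30: √(0.1225² + 0.0973²) = 0.156. With 97 degrees of freedom, the range is 0.023 to 0.094, or 4.0-fold.

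At m = 200, the same steps give SDs of 0.031 and 0.049, and ranges of 0.041 to 0.054 and 0.038 to 0.059.

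**Simulation.** The set-up was 130 per arm, four weekly visits, SD 20 at Week 4, monotone dropout, sequential regression imputation within arm, ANCOVA and Rubin's rule. Visit correlation and dropout timing are assumptions. With about 30% missing and correlations of 0.5 to 0.85, λ was 0.17 to 0.31. The table shows the 95% range of p over seeds on the same data, at correlation 0.7, 31% missing and λ = 0.24.

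| t | m = 20 | fold | m = 200 | m = 1000 |
|---|---|---|---|---|
| 2.0 | 0.025–0.086 | 3.4 | 0.038–0.055 | 0.043–0.049 |
| 2.5 | 0.006–0.030 | 5.1 | 0.010–0.016 | 0.012–0.014 |
| 3.0 | 0.0011–0.0085 | 7.4 | 0.0022–0.0038 | 0.0026–0.0033 |
| 3.6 | 0.0001–0.0016 | 14 | 0.0003–0.0005 | 0.0003–0.0004 |

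At correlation 0.85 with 30% missing, the folds at m = 20 are 2.5, 3.1, 4.0 and 6.2. At correlation 0.7 with 20% missing, they are 2.4, 3.1, 4.2 and 6.4. The formula at λ = 0.24, t = 2.0 gives 0.025 to 0.085, in agreement with the first row.

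**Crossing 0.05.** At t = 2.0 and m = 20, 35% to 48% of seeds gave p above 0.05 across these three settings. At t = 2.1 the formula gives Φ((1.974 − 2.1)/0.101) = 11% for λ = 0.15 and Φ((1.985 − 2.1)/0.160) = 24% for λ = 0.30. With m = 200 both fall below 1%.

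**Against the step between shift levels.** A 10% step is 1 point at the design effect. Applied once to 30% of the arm, it moves the difference by 0.3 points, so t by 0.3/2.96 = 0.10. If the shift cumulates over visits, the simulated step is about 0.3. If each level has its own draws, the noise in the difference between adjacent levels is √2 × 0.099 to √2 × 0.156, or 0.14 to 0.22. A harsher level would then show the larger t with probability Φ(−0.10/0.14) to Φ(−0.10/0.22), about 24% to 33%, for the small step. For the step of 0.3 it is about 2% to 9%.

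**The estimate.** At m = 20 the pooled difference moves between seeds with an SD of 0.23 to 0.40 PANSS points, against a display unit of 0.1.

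**The case against.** No formal decision rests on this analysis. The primary test is the MMRM on observed data (SAP Section 3.8.2.1), the gate to CGI-S uses that test alone (Section 3.8.4), and the sensitivity analysis has no success rule. Rubin's rule already widens the standard error for a finite number of imputations, so m = 20 is noisy but not invalid. A Monte Carlo SD of 0.23 to 0.40 points is small beside an assumed 10-point effect. In a simulated data set near that effect, all 150 reruns stayed below 0.05 at the 10%, 30% and 50% shifts. All of this stands, and it is why the point is minor.

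The inputs also limit the claim. The 30% is a planning dropout rate, and the full analysis set drops subjects with no post-baseline PANSS, so Week 4 missingness may be lower. If the same draws serve all shift levels, the noise is largely shared and the step-to-step comparison loses most of its force. The three-decimal rule is a general display convention, not a claim of Monte Carlo accuracy.

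A reader might infer that p varies by an order of magnitude in general. One simulated data set rerun 60 times at the 50% shift did give 0.0013 to 0.0173, but that is the extreme range, all below 0.05. Its SD of t (0.145) implies a 95% range of about 0.0023 to 0.0125, or 5.4-fold. In the data set near the design effect, the 95% spread was 19-fold at a median p of 0.0007, 13-fold at 0.002 and 9-fold at 0.006, again always significant.

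A reader might also infer that the analysis cannot be reproduced. The documents do not show this: a fixed seed makes a run exactly repeatable, and one may be in the separate programming specifications. A seed does not remove the dependence of the answer on the seed chosen, however.

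**Conclusion.** The point holds in a limited form. With 20 imputations and no seed in the SAP, a delta-adjusted p-value near 0.05 is uncertain by about 2.5- to 4-fold, and the shift level at which significance is lost can be partly a product of the seed. This matters only if the result comes close to 0.05 at one of the shifts. For strong results the relative spread is larger, but the conclusion does not change.

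The size rests on about 30% missing at Week 4, a fraction of missing information of 0.15 to 0.30, and assumed visit correlations and dropout timing, none of which the documents fix beyond the planning dropout rate. Severity is low: a free improvement to a sensitivity analysis.

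**What to change.** In SAP Section 3.8.2.2, raise the number of imputations from 20 to at least 200, and further if a result lies close to 0.05. State one seed in the SAP and use the same imputation draws at all five shift levels. Apply the same rule to the CGI-S analysis in Section 3.8.3. Report the Monte Carlo error, at least √(B/m) for the pooled difference, beside each result.

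A count of 200 reduces the error but does not make the third decimal of p stable, which is why the error should be shown. With 1000, the simulated range at t = 2.0 is 0.043 to 0.049.

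The cost is minutes of computing and a sentence or two in the SAP. The design, the data and the primary analysis stay as they are.
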